8.4.2. Method of Detecting AEs and SAEs

The method of recording, evaluating, and assessing causality of AEs and SAEs and the procedures for completing and transmitting SAE reports are provided in [Appendix 3](#).

Care will be taken not to introduce bias when detecting AEs and/or SAEs. Open-ended and nonleading verbal questioning of the participant is the preferred method to inquire about AE occurrences.

8.4.3. Follow-Up of AEs and SAEs

After the initial AE or SAE report, the investigator is required to proactively follow each participant at subsequent visits/contacts. For each event, the investigator must pursue and obtain adequate information until resolution, stabilization, the event is otherwise explained, or the participant is lost to follow-up (as defined in [Section 7.3](#)).

In general, follow-up information will include a description of the event in sufficient detail to allow for a complete medical assessment of the case and independent determination of possible causality. Any information relevant to the event, such as concomitant medications and illnesses, must be provided. In the case of a participant death, a summary of available autopsy findings must be submitted as soon as possible to Pfizer Safety.

Further information on follow-up procedures is provided in [Appendix 3](#).

8.4.4. Regulatory Reporting Requirements for SAEs

Prompt notification by the investigator to the sponsor of an SAE is essential so that legal obligations and ethical responsibilities toward the safety of participants and the safety of a study intervention under clinical investigation are met.

The sponsor has a legal responsibility to notify both the local regulatory authority and other regulatory agencies about the safety of a study intervention under clinical investigation. The sponsor will comply with country-specific regulatory requirements relating to safety reporting to the regulatory authority, IRBs/ECs, and investigators.

Investigator safety reports must be prepared for SUSARs according to local regulatory requirements and sponsor policy and forwarded to investigators as necessary.

An investigator who receives SUSARs or other specific safety information (eg, summary or listing of SAEs) from the sponsor will review and then file it along with the SRSD(s) for the study and will notify the IRB/EC, if appropriate according to local requirements.

8.4.5. Environmental Exposure, Exposure During Pregnancy or Breastfeeding, and Occupational Exposure

Environmental exposure occurs when a person not enrolled in the study as a participant receives unplanned direct contact with or exposure to the study intervention. Such exposure may or may not lead to the occurrence of an AE or SAE. Persons at risk for environmental

exposure include healthcare providers, family members, and others who may be exposed. An environmental exposure may include EDP, EDB, and occupational exposure.

Any such exposures to the study intervention under study are reportable to Pfizer Safety within 24 hours of investigator awareness.

8.4.5.1. Exposure During Pregnancy

An EDP occurs if:

- A female participant is found to be pregnant while receiving or after discontinuing study intervention.
- A male participant who is receiving or has discontinued study intervention inseminates a female partner.
- A female nonparticipant is found to be pregnant while being exposed or having been exposed to study intervention because of environmental exposure. Below are examples of environmental EDP:
 - A female family member or healthcare provider reports that she is pregnant after having been exposed to the study intervention by ingestion, inhalation, or skin contact.
 - A male family member or healthcare provider who has been exposed to the study intervention by ingestion, inhalation, or skin contact then inseminates his female partner prior to or around the time of conception.

The investigator must report EDP to Pfizer Safety within 24 hours of the investigator's awareness, irrespective of whether an SAE has occurred. The initial information submitted should include the anticipated date of delivery (see below for information related to termination of pregnancy).

- If EDP occurs in a participant/participant's partner, the investigator must report this information to Pfizer Safety using the CT SAE Report Form and EDP Supplemental Form regardless of whether an SAE has occurred. Details of the pregnancy will be collected after the start of study intervention and 28 days after the last dose of study intervention.
- If EDP occurs in the setting of environmental exposure, the investigator must report information to Pfizer Safety using the CT SAE Report Form and EDP Supplemental Form. Since the exposure information does not pertain to the participant enrolled in the study, the information is not recorded on a CRF; however, a copy of the completed report is maintained in the investigator site file.

Follow-up is conducted to obtain general information on the pregnancy and its outcome for all EDP reports with an unknown outcome. The investigator will follow the pregnancy until

completion (or until pregnancy termination) and notify Pfizer Safety of the outcome as a follow-up to the initial report. In the case of a live birth, the structural integrity of the neonate can be assessed at the time of birth. In the event of a termination, the reason(s) for termination should be specified and, if clinically possible, the structural integrity of the terminated fetus should be assessed by gross visual inspection (unless pre-procedure test findings are conclusive for a congenital anomaly and the findings are reported).

Abnormal pregnancy outcomes are considered SAEs. If the outcome of the pregnancy meets the criteria for an SAE (ie, ectopic pregnancy, spontaneous abortion, intrauterine fetal demise, neonatal death, or congenital anomaly in a live-born baby, a terminated fetus, an intrauterine fetal demise, or a neonatal death), the investigator should follow the procedures for reporting SAEs. Additional information about pregnancy outcomes that are reported to Pfizer Safety as SAEs follows:

- Spontaneous abortion including miscarriage and missed abortion should be reported as an SAE;
- Neonatal deaths that occur within 1 month of birth should be reported, without regard to causality, as SAEs. In addition, infant deaths after 1 month should be reported as SAEs when the investigator assesses the infant death as related or possibly related to exposure to the study intervention.

Additional information regarding the EDP may be requested by the sponsor. Further follow-up of birth outcomes will be handled on a case-by-case basis (eg, follow-up on preterm infants to identify developmental delays). In the case of paternal exposure, the investigator will provide the participant with the Pregnant Partner Release of Information Form to deliver to his partner. The investigator must document in the source documents that the participant was given the Pregnant Partner Release of Information Form to provide to his partner.

8.4.5.2. Exposure During Breastfeeding

An EDB occurs if:

- A female participant is found to be breastfeeding while receiving or after discontinuing study intervention.
- A female nonparticipant is found to be breastfeeding while being exposed or having been exposed to study intervention (ie, environmental exposure). An example of environmental EDB is a female family member or healthcare provider who reports that she is breastfeeding after having been exposed to the study intervention by ingestion, inhalation, or skin contact.

The investigator must report EDB to Pfizer Safety within 24 hours of the investigator's awareness, irrespective of whether an SAE has occurred. The information must be reported using the CT SAE Report Form. When EDB occurs in the setting of environmental exposure, the exposure information does not pertain to the participant enrolled in the study, so the information is not recorded on a CRF. However, a copy of the completed report is maintained in the investigator site file.

An EDB report is not created when a Pfizer drug specifically approved for use in breastfeeding women (eg, vitamins) is administered in accordance with authorized use. However, if the infant experiences an SAE associated with such a drug, the SAE is reported together with the EDB.

8.4.5.3. Occupational Exposure

The investigator must report any instance of occupational exposure to Pfizer Safety within 24 hours of the investigator's awareness using the CT SAE Report Form regardless of whether there is an associated SAE. Since the information about the occupational exposure does not pertain to a participant enrolled in the study, the information is not recorded on a CRF; however, a copy of the completed report is maintained in the investigator site file.

8.4.6. Cardiovascular and Death Events

Not applicable.

8.4.7. Disease-Related Events and/or Disease-Related Outcomes Not Qualifying as AEs or SAEs

Not applicable.

8.4.8. Adverse Events of Special Interest

Not applicable.

8.4.8.1. Lack of Efficacy

This section is not applicable because efficacy is not expected in the study population.

8.4.9. Medical Device Deficiencies

Not applicable.

8.4.10. Medication Errors

Medication errors may result from the administration or consumption of the study intervention by the wrong participant, or at the wrong time, or at the wrong dosage strength.

Medication errors are recorded and reported as follows:

Recorded on the Medication Error Page of the CRF	Recorded on the Adverse Event Page of the CRF	Reported on the CT SAE Report Form to Pfizer Safety Within 24 Hours of Awareness
All (regardless of whether associated with an AE)	Any AE or SAE associated with the medication error	Only if associated with an SAE

Medication errors include:

- Medication errors involving participant exposure to the study intervention;
- Potential medication errors or uses outside of what is foreseen in the protocol that do or do not involve the study participant.
- The administration of expired study intervention;
- The administration of an incorrect study intervention;
- The administration of an incorrect dosage;
- The administration of study intervention that has undergone temperature excursion from the specified storage range, unless it is determined by the sponsor that the study intervention under question is acceptable for use.

Whether or not the medication error is accompanied by an AE, as determined by the investigator, such medication errors occurring to a study participant are recorded on the medication error page of the CRF, which is a specific version of the AE page and, if applicable, any associated serious and nonserious AE(s), are recorded on the AE page of the CRF.

In the event of a medication dosing error, the sponsor should be notified within 24 hours.

Medication errors should be reported to Pfizer Safety within 24 hours on a CT SAE Report Form only when associated with an SAE.

8.5. Pharmacokinetics

Blood samples of approximately 4 mL, to provide approximately 1.6 mL of plasma, will be collected for measurement of plasma concentrations of PF-07853578 as specified in the SoA. Instructions for the collection and handling of biological samples will be provided in the laboratory manual or by the sponsor. The actual times may change. The actual date and time (24-hour clock time) of each sample will be recorded.

All efforts will be made to obtain the samples at the exact nominal time relative to dosing. Collection of samples up to and including 10 hours after dose administration that are obtained within 10% of the nominal time relative to dosing (eg, within 6 minutes of a 60-minute sample) will not be captured as a protocol deviation, as long as the exact time of the collection is noted on the source document and the CRF. Collection of samples more than 10 hours after dose administration that are obtained \leq 1 hour away from the nominal time relative to dosing will not be captured as a protocol deviation, as long as the exact time of the collection is noted on the source document and the CRF. This protocol deviation window does not apply to samples to be collected more than 10 hours after dose administration at outpatient/follow-up visits with visit windows.

Samples will be used to evaluate the PK of PF-07853578. Samples collected for analyses of PF-07853578 plasma concentrations may also be used to evaluate safety or efficacy aspects related to concerns arising during or after the study, for metabolite identification and/or evaluation of the bioanalytical method, or for other internal exploratory purposes.

Genetic analyses will not be performed on these plasma samples unless consent for this was included in the informed consent. Participant confidentiality will be maintained.

Samples collected for measurement of plasma concentrations of PF-07853578 will be analyzed using a validated analytical method in compliance with applicable SOPs. Potential metabolites may be analyzed with either validated or exploratory methods.

The PK samples must be processed and shipped as indicated in the instructions provided to the investigator site to maintain sample integrity. Any deviations from the PK sample handling procedure (eg, sample collection and processing steps, interim storage or shipping conditions), including any actions taken, must be documented and reported to the sponsor. On a case-by-case basis, the sponsor may make a determination as to whether sample integrity has been compromised.

Drug concentration information that may unblind the study will not be reported to investigator sites or blinded personnel until the study has been unblinded.

Any changes in the timing or addition of time points for any planned study assessments must be documented and approved by the relevant study team member and then archived in the sponsor and site study files but will not constitute a protocol amendment. The IRB/EC will be informed of any safety issues that require alteration of the safety monitoring scheme or amendment of the ICD.

8.6. Genetics

8.6.1. Specified Genetics

A 4 mL blood PGx sample for DNA isolation will be collected. DNA samples will be analyzed for the purpose of assessing PNPLA3 polymorphism (rs738409). As part of this analysis, genome-wide markers may be used to control for ethnic-based genetic associations. Additionally, these samples may also be used for retrospective evaluation of additional genetic variants associated with variation in PK, biomarker response, or to explore AEs

should these be observed. Samples will be retained for a period of up to 3 years after the end of the study (eg, CSR finalization).

In the event of DNA extraction failure, a replacement genetic blood sample may be requested from the participant.

See [Appendix 5](#) for information regarding genetic research. Details on processes for collection and shipment of these samples can be found in the lab manual and other supporting documentation.

The PGx sample must be processed and shipped as indicated in the instructions provided to the investigator site to maintain sample integrity. Any deviations from the PGx processing steps, including any actions taken, must be documented and reported to the sponsor. On a case-by-case basis, the sponsor may make a determination as to whether sample integrity has been compromised. Any sample deemed outside of established stability, or of questionable integrity, will be considered a protocol deviation.

As part of further understanding the biological response to study intervention, samples may be used for evaluation of other related genotyping as well as development and validation of bioanalytical methods.

Any data outside of PNPLA3 genotyping will be used for internal exploratory purposes and will not be included in the clinical study report.

8.6.2. Retained Research Samples for Genetics

A 4-mL blood sample optimized for DNA isolation Prep D1 will be collected according to the [SoA](#), as local regulations and IRBs/ECs allow.

Retained Research Samples may be used for research related to the study intervention(s). Genes and other analytes (eg, proteins, RNA, nondrug metabolites) may be studied using the retained samples.

See [Appendix 5](#) for information regarding genetic research. Details on processes for collection and shipment of these samples can be found in the lab manual and other supporting documentation.

8.7. Biomarkers

Biomarkers are not evaluated in this study.

8.7.1. Specified Gene Expression (RNA) Research

Specified gene expression (RNA) research is not included in this study.

8.7.2. Specified Protein Research

Specified protein research is not included in this study.

8.7.3. Specified Metabolomic Research

Specified metabolomic research is not included in this study.

8.7.4. Retained Research Samples for Biomarkers

These Retained Research Samples will be collected in this study:

- A 4 mL whole blood Prep B2.5 optimized for serum (at each sampling time as outlined in the [SoA](#)).

Retained Research Samples will be collected as local regulations and IRB/ECs allow according to the [SoA](#).

Retained Research Samples may be used for research related to the study intervention(s). Genes and other analytes (eg, proteins, RNA, nondrug metabolites) may be studied using the retained samples.

See [Appendix 5](#) for information regarding genetic research. Details on processes for collection and shipment of these samples can be found in the lab manual and other supporting documentation.

8.8. Immunogenicity Assessments

Immunogenicity assessments are not included in this study.

8.9. Health Economics

Health economics/medical resource utilization and health economics parameters are not evaluated in this study.

9. STATISTICAL CONSIDERATIONS

Detailed methodology for summary and statistical analyses of the data collected in this study is outlined here and further detailed in the SAP, which will be maintained by the sponsor. The SAP may modify what is outlined in the protocol where appropriate; however, any major modifications of the primary endpoint definitions or their analyses will also be reflected in a protocol amendment.

9.1. Statistical Hypothesis

No formal statistical hypothesis testing will be performed in this study.

9.2. Analysis Sets

For purposes of analysis, the following analysis sets are defined:

Participant Analysis Set	Description
Enrolled	“Enrolled” means a participant’s, or their legally authorized representative’s, agreement to participate in a clinical study

Participant Analysis Set	Description
	following completion of the informed consent process and randomization to study intervention.
Safety analysis set	All participants randomly assigned to study intervention and who take at least 1 dose of study intervention. Participants will be analyzed according to the study intervention they actually received.
PK Concentration Set	All participants randomly assigned to study intervention and who receive at least 1 dose of study intervention and in whom at least 1 plasma concentration value is reported.
PK Parameter Set	All participants randomly assigned to study intervention and who receive at least 1 dose of study intervention and have at least 1 of the PK parameters of interest calculated.

9.3. Statistical Analyses

The SAP will be developed and finalized before any analyses are performed and will describe the analyses and procedures for accounting for missing, unused, and spurious data. This section is a summary of the planned statistical analyses of the primary and secondary and tertiary/exploratory endpoints.

9.3.1. Safety Analyses

All safety analyses will be performed on the safety population (safety analysis set).

AEs, ECGs, BP, pulse rate, continuous cardiac monitoring, and safety laboratory data will be reviewed and summarized on an ongoing basis during the study to evaluate the safety of participants. Any clinical laboratory, ECG, BP, pulse rate, and respiratory rate abnormalities of potential clinical concern will be described. Safety data will be presented in tabular and/or graphical format and summarized descriptively, where appropriate.

Medical history and physical examination and neurological examination information, as applicable, collected during the course of the study, will be considered source data and will not be required to be reported, unless otherwise noted. However, any untoward findings identified on physical and/or neurological examinations conducted during the active collection period will be captured as AEs, if those findings meet the definition of an AE.

Data collected at screening that are used for inclusion/exclusion criteria, such as laboratory data, ECGs, and vital signs, will be considered source data, and will not be required to be reported, unless otherwise noted. Demographic data collected at screening will be reported.

9.3.1.1. Electrocardiogram Analyses

Changes from baseline for the ECG parameters HR, QT interval, QTcF, PR interval, and QRS complex will be summarized by treatment and time. The frequency of uncorrected QT values above 500 ms will be tabulated.

The number (%) of participants with maximum post-dose QTcF values and maximum increases from baseline in the following categories will be tabulated by treatment:

Safety QTcF Assessment

Degree of Prolongation	Mild (ms)	Moderate (ms)	Severe (ms)
Absolute value	>450-480	>480-500	>500
Increase from baseline		30-60	>60

If more than 1 ECG is collected at a nominal time after dose administration (for example, triplicate ECGs), the mean of the replicate measurements will be used to represent a single observation at that time point. If any of the 3 individual ECG tracings has a QTcF value >500 ms, but the mean of the triplicates is not >500 ms, the data from the participant's individual tracing will be described in a safety section of the CSR in order to place the >500 ms value in appropriate clinical context. However, values from individual tracings within triplicate measurements that are >500 ms will not be included in the categorical analysis unless the average from the triplicate measurements is also >500 ms. Changes from baseline will be defined as the change between the postdose QTcF value and the average of the pre-dose triplicate values at -1, -0.5, and 0 hours pre-dose on Day 1.

In addition, an attempt will be made to explore and characterize the relationship between plasma concentration and QT interval length using a PK/PD modeling approach. If a PK/PD relationship is found, the impact of participant factors (covariates) on the relationship will be examined. The results of such analyses may not be included in the CSR.

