2. INTRODUCTION

This statistical analysis plan (SAP) provides the detailed methodology for summary and statistical analyses of the data collected in Study C5161001. This document may modify the plans outlined in the protocol; however, any major modifications of the primary endpoint definition or its analysis will also be reflected in a protocol amendment.

Text in *italics* is taken directly from the protocol.

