2.1. Modifications to the Analysis Plan Described in the Protocol

No modifications.

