5.2.1. Analyses for Continuous Endpoints

Unless otherwise stated, continuous variables will be presented using summary statistics: number of observations, arithmetic mean, standard deviation, median, minimum and maximum values.

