6.1.4. Electrocardiograms

Absolute values and changes from baseline in QT, heart rate, QTcF, PR and QRS will be summarized by dose and treatment (if applicable) and timepoint using sponsor reporting standards, using the safety analysis set defined in Section 4. Baseline is as defined in Section 3.1.4.

Mean changes from baseline in QT, heart rate and QTcF will be plotted against time post-dose. On each plot there will be one line for each treatment. Corresponding individual plots of changes from baseline will also be produced for each treatment.

Changes from baseline in QTcF will also be plotted separately against drug concentrations of PF-07853578. This will be a scatter plot for all observations where QTcF and drug concentration are recorded. Placebo data will also be included (with drug concentration set to zero). Different symbols will be used for each treatment.

Maximum increase from baseline for QTcF, heart rate, PR and QRS values will be summarized by dose and treatment (if applicable) according to sponsor reporting standards.

ECG endpoints and changes from baseline (QTcF, PR and QRS) will also be summarized descriptively by dose and treatment (if applicable) using categories as defined in Appendix 2. Numbers and percentages of participants meeting the categorical criteria will be provided. All planned and unplanned postdose time points will be counted in these categorical summaries.

Values meeting the categorical criteria occurring pre-dose on Day 1 for each period starting with Period 2, will be attributed to the treatment from the previous period (e.g., for cohort 1, an occurrence pre-dose at Period 2 Day 1 will be attributed to the Period 1 dose).

Listings of participants with any single post-dose value >500msec will also be produced for QTcF.

Data collected at screening that are used for inclusion/exclusion criteria, will be considered source data, and will not be required to be reported, unless otherwise noted.

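### Does the SAP drop the protocol's count of uncorrected QT values above 500 ms without saying so?

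*Protocol*

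**What the plan says.** Protocol 9.3.1.1 plans by-treatment summaries of change from baseline for the ECG parameters, including uncorrected QT, and then adds: "The frequency of uncorrected QT values above 500 ms will be tabulated". A separate table of QTcF categories follows. The same section says that replicate ECGs at a nominal time are averaged and treated as one observation.

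The SAP handles uncorrected QT as a continuous variable:

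- SAP 3.1.4 derives change from baseline in QT, but leaves QT out of the maximum post-dose values.
- SAP 6.1.4 summarizes absolute values and changes in QT by treatment and timepoint. The default statistics in SAP 5.2.1 are "number of observations, arithmetic mean, standard deviation, median, minimum and maximum values".
- SAP 6.1.4 also plots QT: "Mean changes from baseline in QT, heart rate and QTcF will be plotted against time post-dose". Individual change plots accompany these.
- The categorical output is narrower: "ECG endpoints and changes from baseline (QTcF, PR and QRS) will also be summarized descriptively by dose and treatment", using the classes in Appendix 2, which has no row for uncorrected QT.
- The remaining output at 500 msec is a listing: "Listings of participants with any single post-dose value >500msec will also be produced for QTcF".

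On its relation to the protocol, SAP section 2 says "This document may modify the plans outlined in the protocol", and SAP 2.1 then says "No modifications".

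**The concern.** The protocol commits to a named output, the SAP does not list it, and the SAP states that nothing has changed. A programmer working only from SAP 6.1.4 and Appendix 2 would not build the table. The 12-lead ECG is part of the primary safety endpoint of a first-in-human study, so an output that disappears without comment deserves a look.

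The QTcF outputs also do not reproduce the count. Below 60 bpm the Fridericia correction pulls the value down, so a QT just above 500 ms sits below the QTcF class above 500. If the table were not produced, a reader could see from the by-timepoint maximum that a QT had exceeded 500 ms, but not directly how many values did so under each treatment.

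**Working it through.** **Inputs.** The formula in SAP 3.1.4 is QTcF = QT / RR^(1/3) with RR = 60/HR, which gives QTcF = QT × (HR/60)^(1/3). The absolute QTcF classes in SAP Appendix 2 are above 450 to 480, above 480 to 500, and above 500 msec. The plan states no figure to reproduce. The documents give no heart-rate distribution, so 40 to 60 bpm is assumed; Protocol Appendix 8 and SAP Appendix 2 flag slow rates only below 40.

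**Step 1: where does a QT of 500 ms land?**

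| HR (bpm, assumed) | QTcF when QT = 500 ms | QT at which QTcF = 500 ms |
|---|---|---|
| 40 | 500 × (40/60)^(1/3) = 436.8 | 572.4 |
| 45 | 454.3 | 550.3 |
| 50 | 470.5 | 531.3 |
| 55 | 485.7 | 514.7 |
| 60 | 500.0 | 500.0 |

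The QTcF class above 500 therefore cannot stand in for the QT count at rates below 60 bpm. That part of the concern is right.

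**Step 2: can a QT above 500 ms escape every absolute QTcF class?** Setting QT = 500 and solving for the rate:

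- QTcF = 450 at HR = 60 × (450/500)^3 = 60 × 0.90^3 = 43.74 bpm.
- QTcF = 480 at HR = 60 × (480/500)^3 = 60 × 0.96^3 = 53.08 bpm.

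At 43.74 bpm or faster, every QT above 500 ms has a QTcF above 450 and is in a tabulated class. Above 53.08 bpm it is in one of the top two classes, and from 60 bpm in the top class. Below 43.74 bpm some values escape. At 40 bpm the QT that gives QTcF 450 is 450 / (40/60)^(1/3) = 515.1 ms, so the gap runs from just above 500 to about 515 ms. For triplicate means these boundaries are approximate, because QT and rate are averaged over three tracings.

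**Step 3: what do the by-timepoint summaries show?** Take six complete active values at a timepoint, the planned number per period. A maximum above 500 ms alone is compatible with 1 to 6 such values. The other SAP 5.2.1 statistics narrow this, since the median of six lies between the third and fourth ordered values:

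- maximum above 500, median at or below 500: 1 to 3 values;
- median above 500, minimum at or below 500: 3 to 5 values;
- minimum above 500: all 6.

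This is not the exact count, but it is more than the maximum alone tells.

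**Step 4: is the protocol sentence still in force?** Protocol section 9 describes the analysis as outlined there and detailed further in the SAP. The SAP may modify it, but declares that it has not. Silence about one table, together with a statement of no modification, leaves that table in the plan.

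**Step 5: can an analyst produce it without inventing rules?** Protocol 9.3.1.1 gives the variable, the threshold and the unit (values), and says to average replicates. SAP 5.2 gives the treatment groups. For its other ECG categories SAP 6.1.4 says "All planned and unplanned postdose time points will be counted in these categorical summaries", which is the natural convention to carry over. QT is measured at every ECG under Protocol 8.3.4.

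**The case for a change.** The strongest case for a change is that SAP 2.1 is a declaration and, read against 6.1.4 and Appendix 2, an inaccurate one. The repair would be a line of text, the protocol itself treats absolute QT as meaningful, and the QTcF tables demonstrably do not give the count.

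Most of this stands as fact. The SAP does not specify the table, and the exact count cannot be recovered from the outputs it does specify. Unplanned ECGs may also fall outside the by-timepoint summaries, although the QTcF categories include them. The sponsor reporting standards cited in SAP 6.1.4 might supply the table, but they are not in the documents and cannot be relied on either way.

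What does not follow is that anything is gained by a change. A line in the SAP would repeat a protocol commitment that already binds. A new row in Appendix 2 would not deliver that commitment, because those categories feed numbers and percentages of participants, while the protocol promises a frequency of values. The protocol's operational use of absolute QT also argues against urgency: under Protocol 8.3.4 a value of 500 ms or more on a scheduled ECG leads to further ECGs at the time, whether or not a table is made later. The withdrawal criteria in Protocol 7.1.2 and the QT-related AE and SAE flags in Protocol Appendix 8 use QTcF.

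**Conclusion.** The text comparison is correct, but no change follows. This is a drafting gap between two documents that remain compatible: the protocol sentence stands, and an analyst can fill the gap from rules already written down.

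The effect is confined to one descriptive count. Sample size, error rates, endpoint definitions and dose-escalation criteria are untouched, and no hypothesis is tested. Even if the table were overlooked, a QT above 500 ms would go unseen in the absolute QTcF classes only at rates below 43.74 bpm, and at 40 bpm only up to about 515 ms; at a scheduled timepoint it would still appear in the QT maximum.

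This rests on three assumptions: heart rates of 40 to 60 bpm as the relevant slow range, the default statistics of SAP 5.2.1 applying to the ECG summaries, and the protocol sentence being read as still in force. The first affects only the size of the gap. Had the SAP expressly withdrawn the table, the third would fail, but it does not do so.
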